2.2.3 Potential risk and benefit evaluation

Smetinib Insulphate capsule is indicated for pediatric patients with neurofibromatosis type I (NF 1) aged 3 years and older with symptomatic, inoperable plexiform neurofibromas (PN). It was approved to list in China on April 28, 2023, and was included in the medical insurance directory on December 13, 2023. Several guidelines, consensus and diagnosis and treatment norms in China recommend selmetinib hydrohydrogen sulfate for the treatment of NF 1-PN. The most common toxicity of selmetinib sulphate capsules are grade 1 and 2 gastrointestinal symptoms (nausea, vomiting, or diarrhea), asymptomatic elevated creatine phosphokinase levels, acnes rash, and paronychia with good safety and tolerability. Therefore, this

clinical study protocol has a low risk of disease progression and serious adverse events on the treatment of NF 1^[14, 15]. At the same time, in the future studies, the investigators will pay more attention to the subjects' systemic condition and tumor treatment condition, and the subjects will also gain some clinical benefit in this study.

3. Study objective and endpoint (list presentation objective (specific issues to be addressed), corresponding to the outcome measures)

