6.4 Concomitant therapy (permitted adjuvant medication, complementary / replacement therapy)

If the subject has hypertension, diabetes, coronary heart disease and other diseases that need long-term drug control, the investigator and the relevant specialist should evaluate the impact of the disease and the relevant study protocol and determine the dose and duration of adjuvant medication.

6.4.1 Rescue (drug, treatment methods, relevant records.....)

The life hazards during the implementation of the clinical study protocol should be implemented in accordance with the clinical rescue plan, such as cardiopulmonary resuscitation, emergency airway management,

emergency surgical treatment, relevant records during hospitalization should be recorded in the medical record system, after discharge should be recorded in the adverse event record form, and the investigator should analyze whether the rescue causes are related to the study and discuss and discuss synchronously in the rescue records.

7. Discontinuation of the study intervention / subject discontinuation and withdrawal*

7.1 Study Intervention discontinuation (reasons / criteria: such as how many adverse events occurred, length of study discontinuation, how data were collected during discontinuation and how to reactivate the study intervention, whether follow-up was continued during discontinuation)

If the Grade 5 adverse event of CTCAE 5.0 standard reaches 10% of the number of subjects, the study should be discontinued, and the drug safety of the study protocol should be discussed to determine whether to adjust the dose of drugs in the study protocol, continue the follow-up during the study suspension, and maintain the follow-up record of the original subject.

7.2 Subjects discontinuation / withdrawal from the study (possible reason for subject discontinuation; involving implantable device, discuss how to remove / replace, obtain alternative materials, later contact with the subject, etc.)

When the subject stops or withdraws from the study due to dissatisfaction with the treatment effect of the study plan or his own economic reasons, he should actively communicate with the subject, encourage the subject to actively treat and help them apply for public welfare funds to complete the treatment. If the subject clearly withdraws, the investigator can continue to complete the follow-up without the study intervention.

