It is likely that: adverse events may be caused by treatment measures. There is a reasonable temporal sequence of event occurrence and treatment measures.

Positive concern: The type of adverse event has been identified as treatment and no other reason

Explanation, such as: medication status and concomitant diseases. The timing of the event strongly suggests causality.

The adverse event severity criteria can be according to the CTCAE 5.0 (US Department of Health and Human Services). Beyond the above criteria list, refer to the following criteria:

Mild: Symptoms or signs but tolerable.

Moderate; discomfort enough to interfere with normal life.

Severe: Normal activities are already impossible.

All information about adverse events, whether mentioned by the patient, found by the investigator, or found by physical examination, laboratory examination, etc., should be recorded on the study medical

record and case report form. During the trial, the time, duration, symptoms, signs, severity, measures taken, outcome and relationship assessment of adverse events should be carefully observed and recorded, and the trial should be appropriately followed up.

Possible adverse events include: medication-related complications; procedure-related complications; and related complications after withdrawal.

The investigator should use medical terms / concepts to record AEs or SAEs. Its type, degree, occurrence time, duration, treatment measures, treatment are recorded in detail. The association of the combination of complications and medication with the study treatment was evaluated. All AEs (including SAEs) should be recorded on the Adverse Event Form for the CRF. Any patient who is treated must be evaluated for toxicity. The occurrence of any adverse events (AEs) should be graded according to the NCI Common AE classification criteria (NCI-CTCAE version 5.0).

9. Data collection and management

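### Section 7.1's only safety trigger is deaths in 10% of an undefined number of subjects, and no rule ties toxicity to holding, reducing or stopping drug in a subject

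*Protocol*

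**What the plan says.** Protocol section 7.1 states a single condition: "If the Grade 5 adverse event of CTCAE 5.0 standard reaches 10% of the number of subjects, the study should be discontinued". The same sentence then calls this a suspension, keeps follow-up going, and has drug safety discussed "to determine whether to adjust the dose of drugs in the study protocol". It does not say whether the subjects counted are those planned, enrolled or treated to date. Section 5.5.1 plans 33.

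On risk, section 2.2.3 says the "clinical study protocol has a low risk of disease progression and serious adverse events". Among the most common toxicities it lists "asymptomatic elevated creatine phosphokinase levels, acnes rash, and paronychia with good safety and tolerability". Section 4.2(2) excludes malignant peripheral nerve sheath tumour and other malignancies.

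On monitoring, section 4.1(10) sets entry limits on CK and LVEF, section 3.2.3 lists both as safety indicators, and the schedule in section 5.2 has rows for heart function and heart ultrasound. Section 8 adds: "Any patient who is treated must be evaluated for toxicity".

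On single subjects, section 7.2 deals with a subject who stops or withdraws "due to dissatisfaction with the treatment effect of the study plan or his own economic reasons".

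**The concern.** A study-wide stopping rule should act at a level of harm that would be surprising given the risk the protocol claims. This one is set at deaths in one subject in ten, for a tumour type the protocol treats as non-malignant and a drug it describes as well tolerated. Followed to the letter on the planned sample, it allows three deaths before anyone is obliged to pause. Because the denominator is open, two readers can apply the same sentence and reach different decisions after the first death.

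Below the level of death, the protocol collects the signals it expects to matter but attaches no action to them. Whether a subject with rising CK or falling LVEF stays on drug, is reduced or stops is then left to each investigator. That is a safety matter, and it makes the tolerability results harder to interpret. Stopping and dosing rules are protocol content, so a statistical analysis plan that is not shown would not be expected to supply them. The analysis of the response rate is not affected.

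**Working it through.** **Inputs.** Trigger 10% (7.1). Calculated sample 29, dropout 10%, planned enrolment 33 (5.5.1). The true fatal-event rates p are assumptions, shown as a range, because the protocol states none.

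**The plan's own figure.** 29 / (1 − 0.10) = 32.2, rounded up to 33. This agrees with section 5.5.1.

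**Deaths needed, by reading of the denominator.**
- Planned 33: 0.10 × 33 = 3.3. Three deaths are 3/33 = 9.1% (no trigger); four are 4/33 = 12.1% (trigger).
- The 29 before dropout: 3/29 = 10.3%, so the third death triggers.
- Treated so far: the first death triggers with up to 10 subjects treated, the second with 11–20, the third with 21–30, the fourth with 31–33.

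**Chance of ever reaching the trigger.** The model is binomial: 33 independent subjects with a common rate p, all followed. With the planned denominator,

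P(X ≥ 4) = 1 − Σ (k = 0 to 3) C(33, k) p^k (1 − p)^(33 − k).

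At p = 5% the terms for k = 0, 1, 2, 3 are 0.1840, 0.3196, 0.2692 and 0.1464. Their sum is 0.9192, so P = 0.0808. The chance of at least one death is 1 − (1 − p)^33.

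| True fatal-event rate | 4 or more deaths of 33 | 1 or more deaths of 33 |
|---|---|---|
| 1% | 0.03% | 28% |
| 2% | 0.4% | 49% |
| 5% | 8% | 82% |

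With subjects treated so far as denominator, checked after each subject in turn, the chances are 10%, 20% and 47% at the same three rates. These are upper values: they assume each outcome is known before the next subject starts, whereas over six 30-day cycles deaths lag enrolment and the denominator grows first.

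**What three unreviewed deaths would mean.** The exact 95% interval for 3/33 runs from 1.9% to 24.3%, so the rule can stay silent on data compatible with a very high fatal-event rate.

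**Search for a subject-level toxicity rule.**
- 4.3: withdrawal is suggested when a subject needs treatment unrelated to the study. This is not a toxicity rule.
- 6.4.1: emergency rescue and its recording.
- 7.1: study-wide only.
- 7.2: the two voluntary reasons quoted above.
- 8: grading, causality and recording, including the measures taken.

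None links a Grade 1–4 event, a CK value or an LVEF value to holding, reducing or stopping the drug.

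**The case against.** The best defence is that investigators will act on toxicity whether or not a table tells them to. Several parts of the protocol support this, and they rule out some stronger readings.

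- A reader might infer that nothing short of death changes treatment. The text does not support that. Section 4.3 gives a subject-level exit when other treatment is needed, and section 8 requires the measures taken for each adverse event to be recorded, which presupposes clinical action. What is absent is a toxicity-based rule.
- A reader might take section 7.2 as the full list of permitted reasons for stopping. It only says how to respond when a subject leaves for either of two reasons. It does not mention toxicity, but it does not close the list.
- The fourth death as trigger is the lenient reading. On a running count the rule can act at the first death.
- One might fault the rule for often failing to fire when the true rate is itself 10%. That treats a threshold on an observed proportion as a test of a true rate. Any such threshold fires roughly half the time at its own value, so this is no evidence of a fault.
- One might add that the 20–50 mg range in 5.2.1 and 6.1 leaves the dose undefined. Dosing by body surface area is meant to give subjects different doses, so the width of the range does not measure error. Section 2.2.3 describes the drug as "indicated for pediatric patients with neurofibromatosis type I (NF 1) aged 3 years and older" while 4.1(1) enrols adults, but whether the labelling settles an adult dose cannot be checked from this document. The missing bands are missing detail and not part of this point.
- The heading of 7.1 mentions "length of study discontinuation, how data were collected during discontinuation and how to reactivate the study intervention", but that is a form prompt, not a commitment of this trial, and the text does answer it in part by continuing follow-up.

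It is also fair that section 4.1(5) enrols tumours invading brain and spine, so some deaths may come from the disease. A review trigger should take causality into account.

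These limits leave the study-wide rule, its open denominator and the absence of a toxicity-based subject rule as they are. Unwritten discretion does not replace any of the three.

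**Conclusion.** The point holds as a safety fault in a stated rule. Section 7.1 relies on one trigger that counts only deaths, at a level out of keeping with the protocol's own account of the risk, over a denominator it does not define. On the planned 33, three deaths bring no pause, and the rule has an 8% chance or less of acting at true fatal-event rates up to 5%. On subjects treated so far, it can act at the first death. These chances rest on the binomial model and the assumed rates; the counts of deaths rest only on the protocol's 10% and 33. Alongside this, no section ties toxicity to action in a single subject, although CK and LVEF are entry criteria and safety indicators. No error in the response-rate analysis or the analysis sets follows from this point.

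**What to change.** Replace the trigger in 7.1 with: *Any Grade 5 event not judged unrelated to treatment (section 8 causality categories) pauses new enrolment and first dosing of new subjects until a documented safety review decides on restart.* This removes the denominator question and filters out deaths judged unrelated to treatment.

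Add to 7.1 a subject-level rule that ties Grade 3–4 toxicity, and the CK and LVEF results already scheduled, to a hold, reduce or stop action. The sponsor sets the thresholds.

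**Cost.** A text amendment and ethics re-approval, with no extra subjects. A safe drug will sometimes be paused. Over 33 subjects the chance is at most 1 − 0.995^33 = 15% at a fatal-event rate of 0.5% and 1 − 0.99^33 = 28% at 1%; these are ceilings because the causality filter can only lower them. Heart ultrasound is ticked in 4 of the 9 schedule columns, against 8 for liver, kidney and heart function, so restarting after an LVEF hold may need a repeat echocardiogram.

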9.1 Case report form / electronic data records

Prior to the study start, the Redcap electronic database / EDC database was established based on the content of the paper version of the case report form.

9.2 Data management (data collection form, data storage carrier: electronic / paper, data integrity inspection, database establishment method, data management system, data quality detection method, definition of data lock library, etc.)

The original data should be uniformly recorded in the study medical records. According to the content of the study medical record, the case report form can be completed in the electronic database to ensure the integrity and accuracy of the information. In order to ensure the accuracy

of the data, the researcher should conduct self-examination no less than twice a year, regularly appoint personnel to the sub-center for project quality control, and accept the examination by the hospital and school management departments. If the data registered in the case report form / electronic database are inconsistent with the original records (study medical records), the investigator shall organize timely verification of the data, modify the wrong part according to the requirements of GCP regulations, and make corresponding explanations if necessary.

10. Ethics requirements

This study complied with the provisions of Good Clinical Practice and the Administration of Investigator-Initiated Clinical Studies (Trial) and the Declaration of Helsinki. This study will be conducted only before the ethics committee of the trial. In the course of the study, the revised protocol must be resubmitted to the Ethics Committee for review, and the investigator must wait until the consent of the Ethics Committee before implementing the new protocol.

Each enrolled patient must sign an informed consent form. Copies of the informed consent form and contact information of the investigator and the ethics committee must be provided to the requested patients*. This study will collect the clinical data and personal information of the research subjects for scientific research, which will involve the privacy rights of the patients. The study participants and the data analysts signed a confidentiality agreement not to disclose the personal patient information and disease-related information to any individuals and institutions unrelated to the study. The collected patient data should be managed to prevent personal privacy leakage.

11. References

